6.1.2 Efficacy Endpoints

eDiary Day

Day in which a subject uses the eDiary.

Migraine Day

A migraine day is any calendar day in which the subject experiences a qualified migraine headache. A qualified migraine headache is defined either as a migraine with or without aura as outlined below:

1. A migraine without aura is defined as a headache lasting continuously for ≥ 4 hours, and meeting criteria a and/or b:
 - a) ≥ 2 of the following pain features:
 - Unilateral
 - Throbbing
 - Moderate to severe
 - Exacerbated with exercise/physical activity
 - b) ≥ 1 of the associated symptoms:
 - Nausea and/or vomiting
 - Photophobia and phonophobia

OR

2. A migraine with aura and meeting criteria c and d:
 - c) The occurrence of ≥ 1 of the following fully reversible aura symptoms:
 - Visual
 - Sensory
 - Speech and/or language
 - Retinal
 - Brainstem
 - d) Aura is accompanied, or followed within 60 minutes, by headache lasting continuously for ≥ 4 continuous hours (see [Appendix C](#)).

If the subject took a triptan or ergot-derivative during aura or to treat headache on a calendar day, then it will be counted as a migraine day regardless of the duration and pain features or associated symptoms.

Monthly Migraine Days

Monthly migraine days is the number of migraine days **between each monthly IP dose normalized to 28 day equivalents**, relative to study day 1 in the first 3 months, between the month 5 and 6 visit, between the month 9 and 10 visit and **between the month 12 and 13 visit**. Hereafter, the corresponding visits for these intervals will be reported/presented as/referred to month 1, month 2, month 3, month 6, month 10 and

month 13 visit, respectively. All available eDiary data for the visits will be used and prorated to 28-day equivalents.

Qualified Headache

A migraine or non-migraine headache which lasts ≥ 4 continuous hours, or a headache of any duration for which acute medication was administered for treatment of headache.

In particular, a qualified headache is:

- a qualified migraine headache (including an aura-only event that is treated with acute migraine-specific medication), or
- a qualified non-migraine headache, which is a headache that lasts continuously for ≥ 4 hours and is not a qualified migraine headache, or
- a headache of any duration for which acute medication is administered.

Headache Day

Any calendar day in which the subject experiences a qualified migraine or non-migraine headache.

Monthly Headache Days

Number of headache days in **between each monthly IP dose intervals and normalized to 28 day equivalent** relative to study day 1 in the first 3 months, or between the month 5 and 6 visit, or between the month 9 and 10 visit, **or between the month 12 and 13 visit. Days without eDiary data are handled by proration according to [Section 9.3](#).**

Migraine Attack

An episode of any qualified migraine headache or episode for which the subject took a triptan or ergot-derivative to treat headache or aura. The following rules will be used for distinguishing an attack

of long duration from two attacks or for distinguishing between attacks and relapses:

- a) A migraine attack that is interrupted by sleep, or temporarily remits, and then recurs within 48 hours after onset of the attack will be considered as one attack and not two.
- b) An attack primarily treated successfully with medication but with relapse within 48 hours **of onset of attack** will be considered as one attack.
- c) **A migraine attack lasting more than 48 hours will be counted as one attack.**

Monthly Migraine Attacks

Number of migraine attacks **between each monthly IP dose and normalized to 28 day equivalent** relative to study day 1 in the first 3 months, or between the month 5 and 6 visit, or between the month 9 and 10 visit or **between the month 12 and 13 visit**. **Days without eDiary data are handled by proration according to [Section 9.3](#)**. For the definition of a migraine attacks, see above.

Fifty Percent Responder Rate

At least 50% reduction from baseline in monthly migraine days. **Percentage change from baseline in monthly migraine days is used to determine 50% responder (see [Section 6.6](#))**.

Monthly Cumulative Hours of Migraine Headache

Cumulative duration of any qualifying migraine headache which occurs during each migraine day **between each monthly IP dose and normalized to 28 day equivalent** relative to study day 1 in the first 3 months, or between the month 5 and 6 visit, or between the month 9 and 10 visit, or **between the month 12 and 13 visit**, regardless of acute treatment use. **Days without eDiary data are handled by proration according to [Section 9.3](#)**.

Monthly Acute Medication Use in Days

Number of days on which medications are used for acute treatment of headache **between each monthly IP dose and normalized to 28 day equivalent** relative to study day 1 in the first 3 months, or between the month 5 and 6 visit, or between the month 9 and 10 visit, or **between the month 12 and 13 visit**. **Days without eDiary data are handled by proration according to [Section 9.3](#)**.

Monthly Acute Migraine-specific Medication Use in Days

Number of days on which migraine-specific medications are used **between each monthly IP dose and normalized to 28 day equivalent** relative to study day 1 in the first 3 months, or between the month 5 and 6 visit, or between the month 9 and 10 visit, or **between the month 12 and 13 visit**. **Days without eDiary data are handled by proration according to [Section 9.3](#)**.

Monthly Average Severity of Migraine Pain

Severity of migraine pain is graded as 1=mild, 2=moderate or 3=severe and was rated as its worst or peak intensity per migraine headache. Monthly average severity of migraine pain was defined as the sum of the severity of each observed qualified

migraine day **between each monthly IP dose and normalized to 28 day equivalent** relative to study day 1 in the first 3 months, or between the month 5 and 6 visit, or between the month 9 and 10 visit, **or between the month 12 and 13 visit** divided by the total number of observed qualified migraine days (**as one record in eDiary with start and end time**) in the corresponding interval. **If less than 14 days of eDiary in each interval is recorded, then the monthly average severity of migraine pain will be set as missing.**

Monthly Average Severity of Migraine Symptoms

Migraine Symptoms include nausea, vomiting, photophobia and phonophobia. Severity of these symptoms is graded as 1=mild, 2=moderate or 3=severe and 0 if not reported for qualified migraine headache. Monthly average severity of each migraine symptom was defined as the sum of the severity of corresponding migraine symptom **between each monthly IP dose and normalized to 28 day equivalent** relative to study day 1 in the first 3 months, or between the month 5 and 6 visit, or between the month 9 and 10 visit, **or between the month 12 and 13 visit** divided by the total number of observed qualified migraine days in the corresponding interval. **If less than 14 days of eDiary in each interval is recorded, then the monthly average severity of migraine symptom will be set as missing.**

CCI

CCI

CCI

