Study Phase: Open-label extension

Indication: Prevention of chronic migraine

Primary Objective: To characterize the safety and tolerability of long-term administration of AMG 334

- Primary Objective of Clinical Home Use (CHU) Substudy: To assess users' ability to administer a full dose of AMG 334 in home-use, using either two prefilled syringes (PFS) or two prefilled autoinjector/pens (AI/pen).

Secondary Objectives:

- To characterize the efficacy of long-term administration of AMG 334 as assessed by:
- Change from baseline in monthly migraine days
- Proportion of subjects with at least 50% reduction from baseline in monthly migraine days
- Change from baseline in monthly acute migraine-specific medication treatment days
- Change from baseline in monthly cumulative hours of headache
- Secondary Objective of CHU Substudy: To assess the safety and tolerability of AMG 334 administered using two 1-mL PFS or two 1-mL AI/pens

For the purpose of primary analysis for secondary and exploratory endpoints in the 20130255 open-label extension (OLE) study, baseline is defined as baseline of the AMG 334 20120295 parent study (from the first day subject used eDiary in baseline at week -4 study visit through the day prior to study day 1). However, change from week 8 through 12 data of the parent study (hereafter referred to as parent study Month 3 data) will also be evaluated.

Hypotheses: The clinical hypothesis is that long-term exposure of AMG 334 will be safe and well tolerated in subjects with chronic migraine

Primary Endpoint: Subject incidence of adverse events

Secondary Endpoints:

- Change from baseline in monthly migraine days at assessment timepoints
- Achievement of at least a 50% reduction from baseline in monthly migraine days at assessment timepoints
- Change from baseline in monthly migraine-specific medication treatment days at assessment timepoints
- Change from baseline in cumulative monthly headache hours at assessment timepoints

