FDA	Food and Drug Administration
FSH	Follicle-stimulating hormone
HDL	High-density lipoprotein
Headache	A migraine or non-migraine headache
Headache Day	Any calendar day in which the subject experiences a qualified migraine or non-migraine headache (initial onset, continuation or recurrence of the headache) lasting ≥ 4 continuous hours, or a headache of any duration for which acute medication (simple analgesics, combination analgesics, triptans, ergot-derivatives, opiates) was administered for treatment of headache pain.
Headache Day with moderate or severe intensity	Any calendar day in which the subject experiences a headache, with headache pain lasting ≥ 4 continuous hours, and a peak severity of moderate to severe, or of any severity or duration if the subject takes a triptan or ergot-derivative for headache pain
ICF	Informed consent form
ICH GCP	International Conference on Harmonisation Tripartite Guideline on Good Clinical Practice
ICMJE	International Committee of Medical Journal Editors
IEC	Independent Ethics Committee
IFU	Instructions for Use
INR	International normalized ratio
IP	Investigational product (ie, AMG 334 or if participating in CHU substudy, AMG 334 in either a PFS or prefilled AI/Pen)
IPIM	Investigational Product Instructional Manual

Abbreviation or Term	Definition/Explanation
IRB	Institutional Review Board
IVR/IWR System	Interactive Voice Response (IVR) / Interactive Web Response (IWR) System; telecommunication / internet technology that is linked to a central computer in real time as an interface to collect and process information.
K_d	The equilibrium dissociation constant
LDH	Lactate dehydrogenase
LDL	Low-density lipoprotein
M	Month
MCH	Mean corpuscular hemoglobin
MCHC	Mean corpuscular hemoglobin concentration
MCV	Mean corpuscular volume
MIDAS	Migraine Disability Assessment
Migraine Attack	
An episode of any qualified migraine headache or episode for which the subject took a triptan or ergot-derivative to treat headache or aura. The following rules will be used for distinguishing an attack of long duration from two attacks, or for distinguishing between attacks and relapses:
 
a) A migraine attack which is interrupted by sleep or temporarily remits, and then recurs within 48 hours after onset of the attack will be considered as one attack, and not two.b) An attack primarily treated successfully with medication but with relapse within 48 hours will be considered as one attack.

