1.2 Secondary

To characterize the efficacy of long-term administration of AMG 334 as assessed by:

- Change from baseline in monthly migraine days
- Proportion of subjects with at least 50% reduction from baseline in monthly migraine days
- Change from baseline in monthly acute migraine-specific medication treatment days
- Change from baseline in monthly cumulative hours of headache

For the purpose of primary analysis for secondary and exploratory endpoints in the 20130255 open-label extension (OLE) study, baseline is defined as baseline of the AMG 334 20120295 parent study (from the first day subject used eDiary in baseline at week -4 study visit through the day prior to study day 1). However, change from week 8 through 12 data of the parent study (hereafter referred to as parent study Month 3 data) will also be evaluated.

- Secondary Objective of CHU Substudy: To assess the safety and tolerability of AMG 334 administered using two 1-mL PFS or two 1-mL AI/pens

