4.1 Study Endpoints

Primary Endpoint

The primary endpoint for the study is subject incidence of adverse events.

Secondary Endpoints

- change from baseline in monthly migraine days at assessment time points
- achievement of at least a 50% reduction from baseline in monthly migraine days at assessment time points
- **change from baseline in monthly acute migraine-specific medication treatment days at assessment time points**
- **change from baseline in cumulative monthly headache hours at assessment time points**

Exploratory Endpoints

Change from baseline in

- monthly migraine attacks at assessment time points
- monthly headache (migraine and non-migraine headache) days at assessment time points
- monthly moderate and severe headache (migraine and non-migraine headache) days at assessment time points
- monthly average severity of migraine pain at assessment time points
- monthly average severity of migraine related symptoms (nausea, vomiting, phonophobia, photophobia) for qualified migraine headaches at assessment time points
- migraine-specific quality of life, as measured by the MSQ, version 2.1 at assessment time points
- migraine-related disability, as measured by the MIDAS at assessment time points
- pain interference with daily activities and migraine-specific impact, as measured by the PROMIS Pain Interference Scale short form and single pain and migraine symptom interference questions at assessment time points
- **change in physical impairment over time as measured by the MPFID**
- **change in impact on everyday activities over time as measured by the MPFID**
- AMG 334 pharmacokinetic (PK) concentration
- monthly acute medication use at assessment time points

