6.6 Arithmetic Calculations

Exposure

For calculations of exposure, dose date refers to receiving dose > 0, but can include partial doses. The non-AE safety treatment group assignments will be based on the durations of IP exposure to AMG 334 70 mg and 140 mg as presented below (see also [Appendix C](#)).

Duration of IP Exposure for Subjects Receiving Only 70 mg or 140 mg

Duration = minimum (last dose date + 27, EOS date) – first dose date + 1.

Duration of IP Exposure for Subjects Receiving Both 70 mg and 140 mg

70 mg duration = minimum (first 140 mg dose date - 1, last 70 mg dose date + 27, EOS date) – first 70mg dose date + 1.

140 mg duration = minimum (last 140 mg dose date + 27, EOS date, date of data cut off) – first 140 mg dose date + 1.

Change from Baseline in Monthly Efficacy Measurement

The change from baseline in monthly efficacy measurement is the monthly efficacy measurement in **between consecutive exposures to IP** prior to the given time point minus the baseline monthly efficacy measurement (see Interval Based on Dose Dates for OLE Phase table presented in [Section 6.4](#)). For example, the change from baseline in monthly migraine days at week 12 will be calculated as:

(Monthly migraine days between week 12 interval start date and week 12 interval end date) – Baseline monthly migraine days

If the baseline or post-baseline value is missing, then the change from baseline is set to be missing.

Following efficacy endpoints will be calculated as above:

Secondary endpoints

- change from baseline in monthly migraine days
- change from baseline in monthly acute migraine-specific medication treatment in days
- **change from baseline in cumulative monthly headache hours**

Exploratory endpoints

- change from baseline in monthly migraine attacks
- change from baseline in monthly headache (migraine and non-migraine headache) days
- change from baseline in monthly moderate and severe headache (migraine and non-migraine headache) days
- change from baseline in monthly average severity of migraine pain
- change from baseline in monthly average severity of migraine related symptoms (nausea, vomiting, phonophobia, photophobia) for qualified migraine headaches
- **Change from baseline in migraine-specific quality of life, as measured by the MSQ, version 2.1**
- **Change from baseline in migraine-related disability, as measured by the MIDAS**

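### The secondary endpoint is named as cumulative headache hours, but the SAP's readable derivations add up migraine-headache hours only

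*SAP*

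**What the plan says.** **The endpoint.** The protocol synopsis and protocol Section 10.1.1.2 list "Change from baseline in cumulative monthly headache hours at assessment timepoints" among four secondary endpoints. The matching objective in protocol Section 1.2 is "Change from baseline in monthly cumulative hours of headache". The protocol glossary defines headache as "A migraine or non-migraine headache". The SAP repeats the objective in Section 2, lists "change from baseline in cumulative monthly headache hours at assessment time points" in Section 4.1, and names "change from baseline in cumulative monthly headache hours" again in Section 6.6 among the endpoints to be calculated.

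**The derivation.** SAP Section 6.1.2 has one readable entry for hours, and its title is limited to migraine headache. It defines the quantity as "Cumulative duration of any qualifying migraine headache which occurs during each migraine day", normalized to 28 days, whether or not acute treatment was used. Appendix C has one readable hours entry, also titled for migraine headache, which adds the durations of calendar-day-migraine-headaches. The proration list in SAP Section 9.3 mentions hours of migraine headache only, but that list is open-ended and is not a derivation.

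**Recorded changes.** SAP Section 11 reports two departures from the protocol: the treatment grouping for efficacy summaries, and the omission of bed days and missed work or school days. Neither concerns headache hours.

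**Treated headaches.** For the route without aura, Section 6.1.2 states: "A migraine without aura is defined as a headache lasting continuously for ≥ 4 hours". The aura route also needs at least 4 hours of headache. A triptan or ergot derivative enters Section 6.1.2 through the day: if taken "during aura or to treat headache on a calendar day, then it will be counted as a migraine day". Appendix C adds a third route by which the headache itself becomes a migraine headache. Any duration is enough, provided the drug was taken on the same date at or before the headache's start.

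**The concern.** Elsewhere the plan keeps migraine and headache apart. Migraine days and headache days are separate endpoints with separate definitions, and the headache-day endpoint spells out that both kinds are included. A reader who meets headache hours in the endpoint list will therefore expect non-migraine hours to be in it. A programmer who follows Section 6.1.2 or Appendix C will leave them out.

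At stake is what one of the four secondary results means. It would be tabulated by visit and treatment group, with a mean and a two-sided 95% confidence interval (SAP Section 10.1), under a name that does not describe it. If non-migraine hours do not move in step with migraine hours, the two quantities can tell different stories about total headache burden.

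**Working it through.** **Step 1. Name against derivation.** Every place that names the endpoint (protocol synopsis, 1.2 and 10.1.1.2; SAP 2, 4.1 and 6.6) says headache. Both readable derivations (SAP 6.1.2 and Appendix C) say migraine headache. Section 6.6 gives only the generic rule of post-baseline value minus baseline, so it does not supply the missing sum. Section 11 does not bridge the gap.

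**Step 2. How the two quantities relate.** Let M be migraine-headache hours and N non-migraine hours per 28 days, with total H = M + N. Then change in H = change in M + change in N, so reporting M under the name of H misses exactly the change in N. The documents give no hours data. The figures below are assumed, starting from M = 60 and N = 40, so H = 100.

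| Later M + N | Change in H | Change in M | Change in H minus change in M |
|---|---|---|---|
| 30 + 70 = 100 | 0 | -30 | +30 |
| 30 + 40 = 70 | -30 | -30 | 0 |
| 30 + 20 = 50 | -50 | -30 | -20 |

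The migraine-only figure is the same in all three rows while the headache figure runs from no change to -50. This shows that the sign of the discrepancy is open. It is not an estimate of its size.

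**Step 3. The rules on single diary records.** The midnight-splitting rule was first checked on Appendix C's own example, a headache from 5 May 08:00 to 7 May 13:00. It gives three pieces, as the SAP describes: 16 + 24 + 13 = 53 hours, so the split loses no time.

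The rules were then applied to assumed records. Section 6.1.2 was read in two ways. In the literal reading, a headache qualifies only by at least 4 hours plus features or aura. In the broad reading, a triptan- or ergot-treated headache also qualifies. Entries are hours counted.

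| Record | All headaches | 6.1.2 literal | 6.1.2 broad | Appendix C |
|---|---|---|---|---|
| 5 h non-migraine, no drug | 5 | 0 | 0 | 0 |
| 6 h within one day, migraine features, drug 1 h after onset | 6 | 6 | 6 | 6 |
| 2 h, drug 30 min after onset | 2 | 0 | 2 | 0 |
| 2 h, drug at onset or 30 min before | 2 | 0 | 2 | 2 |
| 6 h, no features or aura, drug 1 h after onset | 6 | 0 | 6 | 0 |
| Same headache, drug 2 h before onset, same date | 6 | 0 | 6 | 6 |

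The first row is the main point: non-migraine hours count under neither readable derivation, on any reading.

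The last four rows are the minor point. Under the literal reading, Section 6.1.2 and Appendix C part company when the drug is taken at or before onset. Under the broad reading they part company when it is taken after onset. The column for all headaches does not depend on drug timing.

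**The case against.** **Another definition may exist.** Section 6.1.2 ends in blacked-out blocks, and monthly efficacy baselines come from the parent study, whose SAP is not available. This stands, and it limits the point to the readable text. A reader might infer that the plan contains no all-headache definition at all; the documents do not support going that far. Against that, Appendix C's readable diary-calculation entries include only a migraine version of hours, so even a hidden definition would leave that entry to be reconciled.

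**Migraine hours may be what was meant.** That is possible, and nothing readable settles it. A reader might infer a deliberate switch of endpoint; the documents show only an unreconciled name and derivation. If migraine hours were intended, Section 11 is where the change should appear.

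**The treated-headache conflict is secondary.** This stands. Migraine-headache hours are not themselves a listed endpoint, so if all headaches are summed the conflict touches no listed endpoint. A reader might infer that Section 6.1.2 always gives such headaches 0 hours. That rests on the literal reading, and the text is not wholly clean: its entry on qualified headache includes a drug-treated aura-only event among qualified migraine headaches. A disagreement survives either reading, but the cases it affects do not stay the same. A reader might also fear for migraine days or the 50% responder endpoint. Appendix C makes any day with triptan or ergot use a migraine day, so the timing clause does not reach them.

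**The numbers are invented cases.** They are, and nothing in the documents shows how often a drug precedes onset or how many hours are non-migraine.

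**Conclusion.** The mismatch holds on the readable text: the endpoint is headache hours, the derivations give migraine-headache hours, and no change is recorded. Followed as it reads, the SAP would report one quantity under the other's name. The discrepancy equals the change in non-migraine headache hours; its size and direction cannot be computed from the documents.

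The consequence is limited. It concerns one descriptive secondary endpoint, with no hypothesis test or sample-size calculation attached, and the primary safety endpoint is untouched. It is still worth correcting before the analysis, because it decides what a named secondary result means. Confidence is medium, because of the blacked-out text and the unavailable parent-study SAP.

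The disagreement over treated headaches is real but minor, and matters only if migraine-headache hours are reported.

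**What to change.** Make the name and the derivation agree, in one of two ways.

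- **Headache hours intended.** Sum the calendar-day-headache durations that Appendix C already defines, over all headaches, migraine and non-migraine. Use the dose-to-dose intervals of SAP Section 6.4 and prorate to 28 days. Report migraine-headache hours, if wanted, as a separately named variable.
- **Migraine hours intended.** Rename the endpoint throughout and record the change in SAP Section 11.

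Either way, apply one rule to the parent-study baseline, the parent-study month 3 values and the extension intervals. Those parent-study values need re-deriving only if they were computed differently, which cannot be seen from these documents.

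If migraine-headache hours are reported under either option, reconcile Section 6.1.2 with Appendix C's third route and state one counting rule for triptan- or ergot-treated headaches.

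The cost is SAP wording and, under the first option, one additional summed variable from durations already derived. No new data collection is needed for the extension study.

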9.3 Handling of Missing and Incomplete Data

Subjects may miss specific data points for a variety of causes. In general, data could be missing due to a subject's early withdrawal from study, a missed visit, or inability to evaluate an endpoint at a particular point in time. For this study, most of the efficacy endpoint will be collected via eDiary and subjects could miss entering several days of data **in between exposures to IP**. The general procedures outlined below describe what will be done when a data point is missing.

Missing eDiary data in the calculation of monthly measurements about subjects' migraine and non-migraine headaches will be handled **using method below**. Unless otherwise specified, all the final analysis and sensitivity analysis will use monthly measurements calculated as follows:

1. **For monthly intervals with ≥ 14 days of eDiary days (days subjects use eDiary and including retrospective eDiary days) in each interval:**
 - a) Monthly frequency measurements (including migraine days, headache days, migraine attacks, cumulative hours of migraine headaches, cumulative hours of migraine headaches with severe pain, acute medication use, etc.) will be

prorated to 28-day equivalents. **Prorated result does not need to be rounded.**

- b) Monthly average severity of migraine pain, migraine related symptoms, **physical impairment scores and impact on everyday activities scores as measured by MPFID** and monthly average scale of migraine interference with daily activity will be calculated as the average of observed scores.
2. **For monthly intervals with < 14 days of eDiary use (including retrospective eDiary days)**, all monthly measurement will be set as missing and will be handled as described in [Section 9.3.2](#)

An information day is a calendar day which is either an eDiary day or headache day and will be used toward headache day proration. The eDiary days will be used toward migraine day proration and medication use day proration.

Missing PROs (MSQ, MIDAS) collected at office visit at certain assessment will not be imputed.

Missing safety endpoints will not be imputed. **Missing day portion of AE start time will be imputed based on [Section 9.3.1](#).**

Missing pharmacokinetic and antibody data will not be imputed.

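### SAP 6.1.2 normalises the sum in the two monthly average severity endpoints to 28 days but not the denominator, which conflicts with SAP 9.3 item 1b and can give values outside the scale

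*SAP*

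**What the plan says.** The protocol lists both severity measures as exploratory endpoints (10.1.1.3) but gives no formula. The formulas are in the SAP, in two places.

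**SAP 6.1.2, pain.** The scale is stated as "Severity of migraine pain is graded as 1=mild, 2=moderate or 3=severe". The monthly value is "defined as the sum of the severity of each observed qualified" migraine day, taken "between each monthly IP dose and normalized to 28 day equivalent relative to study day 1", and then "divided by the total number of observed qualified migraine days" in the same interval.

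**SAP 6.1.2, symptoms.** The scale has an added zero: "Severity of these symptoms is graded as 1=mild, 2=moderate or 3=severe and 0 if not reported for qualified migraine headache". The monthly value is "defined as the sum of the severity of corresponding migraine symptom between each monthly IP dose and normalized to 28 day equivalent", again over observed qualified migraine days.

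Both definitions set the value to missing when fewer than 14 eDiary days are recorded in the interval.

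**SAP 9.3.** For intervals with at least 14 eDiary days, item 1a prorates frequency measures to 28 days. Item 1b covers average pain severity and symptom severity, which "will be calculated as the average of observed scores". No proration is mentioned there.

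SAP 6.6 lists both measures for change from baseline. The visible text of Appendix C has no algorithm for average severity, and Section 11 does not mention the point.

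**The concern.** Proration suits a count: if half the days are unobserved, the observed count understates the month. An average over observed migraine days needs no such correction, because missing days drop out of both the sum and the divisor. As worded, 6.1.2 scales the sum and leaves the divisor as observed days, so the result is the true average times a factor that has nothing to do with severity.

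The SAP therefore carries two rules for the same endpoints, and it is not clear which one governs. If 6.1.2 were programmed, two subjects with identical headaches but different diary completion or dose spacing would get different severity scores. The difference would pass into the change-from-baseline summaries.

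**Working it through.** The documents state no figure to reproduce, so the check is direct algebra.

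**Inputs**
- Scales: pain 1 to 3, symptoms 0 to 3 (SAP 6.1.2).
- Minimum for a non-missing value: 14 eDiary days (SAP 6.1.2 and 9.3).
- Interval length: SAP 6.4 runs most intervals from one dose date to the day before the next. Protocol 7.1 gives each visit a window of ±4 days. When both ends can move, the length runs from 28 − 8 = 20 to 28 + 8 = 36 days.
- Divisor for normalising: not stated for severity. *Assumption:* D, the number of eDiary days in the interval, which is what 9.3 uses for migraine-day proration.

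**Formulas.** Let S be the sum of observed scores, M the observed qualified migraine days, and m = S / M.
- 6.1.2 read literally: (S × 28/D) / M = m × 28/D
- 9.3 item 1b: S / M = m

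**Results**

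| D | 28/D | m = 1 | m = 2 | m = 2.5 | change at constant severity 2, baseline 2.0 |
|---|---|---|---|---|---|
| 14 | 2.00 | 2.00 | 4.00 | 5.00 | +2.00 |
| 20 | 1.40 | 1.40 | 2.80 | 3.50 | +0.80 |
| 24 | 1.17 | 1.17 | 2.33 | 2.92 | +0.33 |
| 28 | 1.00 | 1.00 | 2.00 | 2.50 | 0 |
| 32 | 0.875 | 0.88 | 1.75 | 2.19 | −0.25 |
| 36 | 0.78 | 0.78 | 1.56 | 1.94 | −0.44 |

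The literal value exceeds 3 whenever m > 3D/28, that is, above 1.5 at D = 14, above 2.14 at D = 20 and above 2.57 at D = 24. At D = 36 an all-mild pain month (m = 1) gives 0.78, below the pain minimum of 1. For symptoms 0.78 is still inside the 0 to 3 range, though wrong. The last column assumes a baseline value of 2.0. Under 9.3 item 1b every entry in that column is 0.

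**Variant 1: both terms normalised.** Ten migraine days all rated 2 with D = 14 give (20 × 2) / (10 × 2) = 2.0. The factor cancels and the 9.3 value returns.

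**Variant 2: normalising by interval length.** For 20 to 36 days the factor runs from 28/20 = 1.4 to 28/36 = 0.78. Missed diary days then have no effect, but a mean of 2.5 still becomes 3.5 in a 20-day interval.

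**The case against.** The strongest reply is that the normalisation words are carried over from the neighbouring count definitions, where they belong, and that 9.3 holds the operative rule. The layout supports this. The definitions of headache days, attacks, hours and medication days each point to 9.3 for proration, while the two severity definitions carry only the 14-day missing rule. A programmer working from 9.3 would get the right value. The pain numerator also refers to observed days, so the words could be read as describing the interval or both terms, and then nothing is distorted.

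This explains how the wording probably arose, but it does not settle which rule applies. SAP 9.3 presents its rules as defaults that give way where something else is specified, and 6.1.2 can be read as specifying something else. If the factor was meant to cancel, the words do no work and should still go.

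Three parts of the reply stand:
- The size depends on a divisor that the SAP does not name.
- No diary compliance figures are given, so the typical distortion is unknown. At about 28 diary days there is almost none.
- Baseline comes from the parent study, whose SAP is not among the documents. Whether the same formula was used there cannot be checked.

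**Conclusion.** The conflict between SAP 6.1.2 and 9.3 item 1b is real, and the rule in 6.1.2, read literally, is wrong for an average. On that reading, and assuming a factor of 28 divided by eDiary days, the average is multiplied by anything from 2.0 (14 days) to about 0.78 (36 days). It can leave the scale at the top for both measures and at the bottom for pain.

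Four stronger inferences are tempting, and the documents do not support them:
- *That the endpoint would measure missing diary days in place of severity.* The literal value is the true mean times a factor, so severity is contaminated and not replaced.
- *That the error only inflates, by 1.0 to 2.0.* Dose intervals longer than 28 days push the factor below 1.
- *That out-of-range values will certainly be reported.* This holds only if 6.1.2 is programmed literally and 9.3 is not followed.
- *That the main results are at risk.* Both measures are exploratory (SAP 4.1), summarised descriptively with no formal tests (SAP 10.1). The primary safety endpoint and the secondary endpoints do not use this formula.

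This is a minor correction, but it concerns a wrong rule in an endpoint definition and not just missing detail.

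**What to change.** In both severity definitions in SAP 6.1.2, delete the normalisation words (the part of "between each monthly IP dose and normalized to 28 day equivalent" that follows the reference to the IP dose). Refer both definitions to 9.3 item 1b: average of observed scores, missing if fewer than 14 eDiary days.

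State the denominator as the qualified migraine days that have an observed score. This matters because Appendix C counts a day with triptan or ergot use as a migraine day even without a headache, and such a day may carry no pain score. The parenthesis in the pain definition about eDiary records with start and end times goes part of the way, but the symptom definition has no equivalent.

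The cost is a short text edit in two definitions, plus confirmation that the analysis programs follow 9.3 item 1b. Data collection and study conduct do not change.
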